A directed physical examination will be performed at each visit and recorded in the physical examination case report form via the tablet into the database.

Sputum for smear, GeneXpert and TB culture will be collected at the baseline, week 8 and week 24 visits by asking the participant to cough and collect expectorated sputum in a sputum container, while seated at a sputum collection booth, which is fitted with a high-efficiency particulate arrestance (HEPA) filter for infection control purposes.

CXRs will be performed on all participants at baseline. At week 8 and 24 only those who were diagnosed on CXR, where the radiographic treatment response pattern is required and those in whom a follow-up CXR is ordered by a clinician for clinical reasons, will have follow-up x-rays.

Any clinical information or test results that could potentially impact a participant's clinical care, will be shared with the participant's local clinic.

Rapid HIV tests will be performed on all participants with previously negative or unknown HIV status, after pre-test counselling. Results will be given to participants, along with post-test counselling. A negative result will be considered negative, while a positive result will be confirmed by a second rapid test from a different manufacturer. Incongruent results will finally be confirmed by an HIV Elisa. Newly diagnosed HIV infected participants will receive a CD4 count and be referred to their local clinic for possible antiretroviral treatment.

Blood, sputum, urine and saliva samples will be collected at baseline, week 8 and 24, and additionally at week 2 if clinically indicated for TB diagnosis.

The table below outlines the sample types, volumes, frequency and other investigations performed.

Version 0.3 May 2016

| Sample collection and Inves | stigations performed | | | | | |
|---|---|------------------------------|--|---|---------------------------------|---|
| | | | Participant group and Time Point | | | |
| | | | Baseline | We | Week 24 | |
| Sample type | Processing and analysis destination | Sample volume | All | TB arm | Non-TB arm | TB arm |
| Whole blood in Serum Seperator Tube (SST) | Serum separation for ELISA, Luminex, TransDot optimisation and laboratory-based evaluation, storage in study specific bio-repository | 10 ml | Yes | Yes | Yes | Yes |
| Whole blood in Sodium Heparin tube | Peripheral blood mononuclear cell isolation for future biomarker discovery work | 2 x 8 ml = 16ml | Yes | Yes | No | Yes |

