| Whole blood 4 QFN tubes | Quantiferon Gold test | 4 x 1ml = 4ml | Yes | No | No | No |
| Whole blood in PAXgene tube | Future whole blood RNA signature discovery work | 2.5ml | Yes | Yes | No | Yes |
| Fingerprick blood | HIV rapid test | 1 to 2 drops | Yes | No | No | No |
| Whole blood in EDTA tube | CD4 count | 2 ml | New HIV diagnosis only | No | No | No |
| Fingerprick blood | POC TransDot test in Test set participants | 1 to 2 drops | Yes (Test set) | Yes (Test set) | No | Yes (Test set) |
| TOTAL BLOOD VOLUME | Total volume over 24 weeks for TB arm: 89.5 ml (+2 ml for CD4 in some) Total volume over 8 weeks for non-TB arm: 42.5 ml (+ 2ml for CD4 in some) | | 32.5ml (+ 2ml for CD4 in some) | 28.5 ml | 10 ml | 28.5 ml |
| Sputum | AFB smear | 1 ml | Yes | Yes | Only if clinically indicated | Yes |
| Sputum | GeneXpert | 1 ml | Yes | No | Only if clinically indicated | No |
| Sputum | Culture | 1 ml | Yes | Yes | Only if clinically indicated | Yes |
| Sputum | Future sputum-based diagnostic or treatment response investigations, including GeneXpert Ultra and new culture techniques | 2 x 1ml for storage | Yes | Yes | No | Yes |
| Induced sputum (hypertonic saline nebulisation) | Diagnostic or Future sputum-based diagnostic or treatment response investigations, including GeneXpert Ultra and new culture techniques | Up to 5ml as necessary | If not enough sputum spontaneously | If not enough sputum spontaneously | No | If not enough sputum spontaneously |
| Saliva from two salivettes chewed | Stored for future biomarker discovery work | 2 x 1ml | Yes | Yes | No | Yes |
| Urine | Stored for future biomarker work | 10 ml | Yes | Yes | No | Yes |
| Urine | Urine pregnancy test in women | Dipstix | Yes, women | No | No | No |
| CXR | Diagnosis and treatment response evaluation | | Yes | Only if indicated for treatment response | Only if clinically indicated | Only if indicated for treatment response |

Sample types and investigations per timepoint

Fingerprick TransDot test

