Collect 10ml blood for serum separation for laboratory based TransDot testing (Training and Test cohort).

Collect 4ml for Quantiferon (QFN) Gold test

Collect 16ml of blood for peripheral blood mononuclear cell (PBMC) isolation.

Collect 2.5ml of whole blood into PAXgene tubes for the study-specific biorepository.

Collect 2ml of saliva into the study-specific biorepository.

Collect 10ml urine into the study-specific biorepository.

Perform POC TransDot test and record the result (Test cohort).

Assure that all participants with symptoms of TB have attended the government clinic to obtain routine TB investigations.

Week 2 visit (only participants not diagnosed with TB by the baseline visit GeneXpert or sputum smear)

Conduct TB symptoms questionnaire and judge whether any symptoms improved or resolved on course of antibiotics for GeneXpert or smear negative patients.

Week 8 visit (all participants)

Conduct TB symptoms questionnaire.

Obtain relevant medical history.

Perform directed physical examination.

Perform CXR (only when indicated for treatment response).

Collect sputum samples for TB sputum smear (except if smear result is available from the government clinic), MGIT culture and storage (only participants on TB treatment or those for whom it is clinically indicated).

Collect 10 ml blood for serum separation for laboratory based TransDot testing (Training cohort).

Collect 16ml of blood for PBMC isolation (participants on TB treatment only).

Collect 10ml urine into the study-specific biorepository (participants on TB treatment only).

Perform POC TransDot test and record the result (Test cohort participants on TB treatment only).

Week 24 visit (only participants who started TB treatment)

Conduct TB symptoms questionnaire.

Obtain relevant medical history.

Perform directed physical examination.

Collect sputum samples for TB sputum smear (except if smear result is available from the government clinic), MGIT culture and storage.

Perform induced sputum if inadequate sputum volumes are available.

Perform CXR (only when indicated for treatment response).

Collect 10 ml blood for serum separation for laboratory based TransDot testing (Training and Test cohort). Collect 16ml of blood for PBMC isolation.

Collect 2.5ml PAXgene tube for study-specific biorepository.

Collect 2ml saliva for study-specific biorepository.

Collect 10ml urine into the study-specific biorepository.

Perform TransDot test and record the result (Test cohort).

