6.3.2.2 SPECIMEN SHIPMENT

Shipment of a total of 374 serum samples from each site (a projected recruitment of 160 participants per site of which one third (53) have active TB with 3 time points for TB cases and 2 for non-TB cases) to LUMC will take place. Shipments will occur at approximately 6-monthly intervals and each shipment will contain the samples obtained during the preceding 6-month period. Shipments might also contain fewer samples if the aims to align TransDot assay performance with ELISA or Luminex have been achieved. Shipment will be done according to International Air Transport Association (IATA) approved procedures and through accredited shippers of biohazardous materials and all Material Transfer Agreements, export and import permits will be in place. Shipments will be temperature controlled. Appropriate contact details of senders and receivers of shipments will be noted on shipping documents.

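### The section 6.2 week 8 list omits PAXgene and saliva and limits serum to the training cohort, in conflict with the section 6.1 sample table and the figures built on it

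*Combined protocol and SAP*

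**What the plan says.** **Section 6.1, text and sample table.** The text states: "Blood, sputum, urine and saliva samples will be collected at baseline, week 8 and 24". In the table, 10 ml of blood for serum is marked Yes at baseline, at week 8 in both arms and at week 24, with no restriction to either cohort. The PAXgene row reads "Future whole blood RNA signature discovery work | 2.5ml | Yes | Yes | No | Yes"; the columns after the volume are baseline, week 8 TB arm, week 8 non-TB arm and week 24. Saliva (2 x 1 ml) has the same pattern. The total blood row reads "32.5ml (+ 2ml for CD4 in some) | 28.5 ml | 10 ml | 28.5 ml", with overall totals of 89.5 ml (TB) and 42.5 ml (non-TB).

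**Section 6.2, visit lists.** The baseline serum line is "Collect 10ml blood for serum separation for laboratory based TransDot testing (Training and Test cohort", and the week 24 line names the same two cohorts. The week 8 line is "Collect 10 ml blood for serum separation for laboratory based TransDot testing (Training cohort". Baseline and week 24 both list PAXgene and saliva (at week 24: "Collect 2.5ml PAXgene tube for study-specific biorepository" and "Collect 2ml saliva for study-specific biorepository"). The week 8 list has neither. It does keep PBMC blood, urine and stored sputum for participants on TB treatment, and the fingerprick TransDot for test-cohort participants on treatment.

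**Section 6.3.2.2.** Each site ships 374 serum samples, based on 160 participants, 53 of them with TB, and "3 time points for TB cases and 2 for non-TB cases".

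**Section 4.** The test-set laboratory TransDot on serum is placed at baseline only.

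**Section 11.2.** PAXgene blood and saliva are to be stored for each participant at each visit.

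**The concern.** Two parts of the protocol give different week 8 sample sets, and nothing says which governs. A nurse working from the 6.2 list would draw PBMC tubes from a test-set TB participant at week 8 but no serum or PAXgene tube, and would collect no saliva. A nurse working from the 6.1 table would collect all of them. With sites in five countries, which samples exist could depend on which passage a site follows, and a sample not taken at week 8 cannot be recovered.

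Week 8 matters because it is the only scheduled mid-treatment sampling visit for TB cases: week 2 is for participants not yet diagnosed, and section 4 puts week 24 at the end of treatment. Section 6.3.2 plans RNA work on PAXgene samples during treatment. Two secondary objectives in section 3, finding additional marker signatures and collecting host samples for future research, draw on these specimens.

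**Working it through.** **Inputs.** Tube volumes are from the 6.1 table: serum 10 ml, PBMC 16 ml, Quantiferon 4 ml, PAXgene 2.5 ml. Cohort sizes are from section 4 (500 training, 300 test). Sections 6.1 and 10.2 expect about one third to have TB. Section 6.3.2.2 gives 160 participants per site.

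**Step 1: reproduce the stated figures from the table.**
- Baseline: 10 + 16 + 4 + 2.5 = 32.5 ml.
- Week 8, TB arm: 10 + 16 + 2.5 = 28.5 ml. Week 8, non-TB arm: 10 ml. Week 24: 28.5 ml.
- TB total: 32.5 + 28.5 + 28.5 = 89.5 ml. Non-TB total: 32.5 + 10 = 42.5 ml.
- Shipment per site: 53 x 3 + 107 x 2 = 159 + 214 = 373. With an exact third it is 373.3, which rounds up to the stated 374.

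All agree. They require a week 8 serum from every participant and a week 8 PAXgene tube from every TB case.

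**Step 2: blood volumes with 6.2 as written.**

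| Participant | Week 8 blood | Total | Stated total |
|---|---|---|---|
| Training, TB | 10 + 16 = 26 ml | 32.5 + 26 + 28.5 = 87.0 ml | 89.5 ml |
| Test, TB | 16 ml | 32.5 + 16 + 28.5 = 77.0 ml | 89.5 ml |
| Training, non-TB | 10 ml | 42.5 ml | 42.5 ml |
| Test, non-TB | 0 ml | 32.5 ml | 42.5 ml |

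**Step 3: serum per site with 6.2 as written**, assuming an even split over five sites (100 training, 60 test) and one third with TB.
- Training: 100/3 x 3 + 200/3 x 2 = 233.3.
- Test: 20 x 2 + 40 x 1 = 80.
- Sum: about 313, against 373.3. The shortfall is 60 per site and 300 overall, one for each test-set participant. That shortfall does not depend on the TB fraction.

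**Step 4: samples at stake at week 8.**
- PAXgene and saliva: 800/3, about 267 TB cases.
- Serum: 300 test-set participants, of whom 300/3 = 100 have TB and 200 do not.

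**Step 5: which figure supports which sample.** The blood volumes depend on serum and PAXgene. The shipment count depends on serum only. Saliva enters neither, so its conflict is with the 6.1 table and text and with section 11.2.

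**The case against.** The best counter-argument concerns serum. Section 4 places the test-set laboratory TransDot at baseline only, so the week 8 training-cohort limit may be deliberate and the week 24 line naming both cohorts may be the outlier. Section 6.3.2.2 also allows for smaller shipments, and section 11.2 ties serum held at the Leiden laboratory to at most 500 participants. This stands: test-set week 8 serum cannot be presumed to be an omission. It does not settle the matter, because 6.2 itself takes test-cohort serum for laboratory TransDot at week 24, and the table and blood totals assume it at both visits.

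No comparable explanation exists for PAXgene and saliva. No passage supports dropping them at week 8 alone.

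A reader might go further and infer that the month 2 part of the agreement objective is lost, because the week 8 fingerprick reading would have no serum counterpart. The documents do not support that. Neither section 3 nor section 10.1 names a month 2 agreement analysis, 6.2 collects baseline serum from both cohorts, and TransDot can be compared with ELISA on training-set serum. Nor is the month 2 treatment-response objective damaged: the week 8 fingerprick test is kept, and section 6.1 compares it with sputum, radiology and symptoms, not with serum assays.

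It would also be too strong to say that marker discovery loses month 2 altogether. PBMC, urine and stored sputum remain for TB cases, as does serum from about 167 training-set TB cases (500/3). Section 6.3.2 describes on-treatment use for PAXgene and PBMC, but describes saliva only in diagnostic terms. Finally, it is an assumption that staff would follow 6.2 rather than the table.

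**Conclusion.** The contradiction is real and should be corrected. Its reach is limited to secondary objectives. If 6.2 is followed, the study loses the only mid-treatment PAXgene and saliva samples in about 267 TB cases, and week 8 serum in up to 300 test-set participants. This partly weakens the additional-marker and sample-collection objectives. The primary endpoint and the 300-participant test set are unaffected.

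For PAXgene and saliva, the table, the 6.1 text (for saliva), section 11.2 and, for PAXgene, the blood volumes all point to collection at week 8. For test-set serum the passages divide, and only the sponsor can say which was meant. The counts assume one third with TB and full week 8 attendance, so they are upper figures. The 313 per site also assumes an even split over sites.

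**What to change.** 1. Add 2.5 ml PAXgene and 2 ml saliva to the 6.2 week 8 list for participants on TB treatment. This costs two lines of text, no extra visit and no blood beyond the 28.5 ml already stated.

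2. Reconcile sections 4, 6.1, 6.2 and 6.3.2.2 on test-set serum, in one of two ways:
   - **Extend the week 8 line to the test cohort.** The table, blood totals and shipment count then stand. Section 4 should state what the later test-set serum is for. The cost is a week 8 blood draw for about 200 test-set non-TB participants that 6.2 does not now list.
   - **Keep the training-cohort limit.** Then restrict the table's serum row by cohort and correct the totals. With PAXgene restored, test-set TB participants have 16 + 2.5 = 18.5 ml at week 8 and 32.5 + 18.5 + 28.5 = 79.5 ml overall, and test-set non-TB participants have 32.5 ml. The shipment count becomes about 313 per site. If the baseline-only wording in section 4 is also meant to remove test-set serum at week 24, a further 20 per site go, leaving about 293, and the 6.2 week 24 line and blood totals need correcting too.

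3. State which passage governs sample collection, so that sites do not diverge.

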6.3 LABORATORY EVALUATIONS

6.3.1 LABORATORY EVALUATIONS/ASSAYS

Sputum will be collected according to standard protocols for GeneXpert (1ml), mycobacterial growth indicator tube (MGIT) (1ml) and performance of direct smears for acid-fast bacilli (1ml), if smear results cannot be accessed from department of health facilities. Any remaining sputum will be used either for cryostorage for the study-specific biorepository (we will aim for 2x1ml aliquots) or performance of new microbiological tests, including GeneXpert Ultra and the detection of extracellular mycobacterial deoxyribonucleic acid (DNA). We will share the findings of our routine diagnostic tests with the clinics, who will remain responsible for treatment decisions and management.

Any future use of sputum samples will be restricted to detection of mycobacterial or host molecules in the context of TB diagnostic or biomarker research.

6.3.2 SPECIMEN COLLECTION, PREPARATION, HANDLING AND SHIPPING

Serum (approximately 5ml) will be obtained through centrifugation of 10ml of whole blood. Serum aliquots of 500µl each will be stored at minus 80 °C until either shipment to Leiden University Medical Centre for direct comparison between TransDot tests and ELISA or Luminex for host markers or investigation by multiplex cytokine array technology or ELISA for host markers with diagnostic potential.

Peripheral blood mononuclear cells will be isolated through the Histopaque/Ficoll Density Media method and stored in liquid nitrogen until further use. The future experiments will be aimed at detection of surface markers or intracellular markers on different immune cells to investigate differences between active TB cases and non-TB cases and to track changes during treatment.

PAXgene tubes will be stored at minus 80 °C until use. RNA will subsequently be extracted to investigate the gene expression profile of immune cells during active TB and during treatment to compare this to non-TB cases. There have been recently described gene expression biosignatures with promise as diagnostic tests but such signatures will require validation in different cohorts.

Sputum aliquots for future use, will be stored raw and in Trizol at minus 80 °C.

Saliva will be stored at minus 80 °C until use. We have previously found promising diagnostic biosignatures in saliva that are made up of host inflammatory markers and these observations require validation in larger studies.

Urine (10ml) will be stored at minus 80 °C for future biomarker investigations.

6.3.2.1 INSTRUCTIONS FOR SPECIMEN PREPARATION, HANDLING AND STORAGE

Specimens will be prepared, handled and stored according to our established SOPs. Serum will be transported at room temperature, saliva, PAXgene tubes and sodium heparin tubes (for peripheral blood mononuclear cell isolation) on ice.

All sample tubes will only be labelled with study-specific participant identifiers (bar codes) and will not contain any personal identifiers. Similarly, tubes for storage will only be marked by unique study and participant-specific codes and not with personal identifiers. The identities of participants can only be linked back to the names of individuals through the consent form, which contains the link between personal identifiers and study ID. Informed consent documents and source documentation will be stored in the regulatory file and participant files in access controlled, locked cabinets at the study site.

6.3.2.2 SPECIMEN SHIPMENT

Shipment of a total of 374 serum samples from each site (a projected recruitment of 160 participants per site of which one third (53) have active TB with 3 time points for TB cases and 2 for non-TB cases) to LUMC will take place. Shipments will occur at approximately 6-monthly intervals and each shipment will contain the samples obtained during the preceding 6-month period. Shipments might also contain fewer samples if the aims to align TransDot assay performance with ELISA or Luminex have been achieved. Shipment will be done according to International Air Transport Association (IATA) approved procedures and through accredited shippers of biohazardous materials and all Material Transfer Agreements, export and import permits will be in place. Shipments will be temperature controlled. Appropriate contact details of senders and receivers of shipments will be noted on shipping documents.

7. DATA MANAGEMENT PLAN

7.1 DATA COLLECTION

Participant information will be collected directly into electronic case report forms by research nurses using tablet computers, equipped with the Research Electronic Data Capture (REDCap) application for this purpose. X-ray report forms will be captured in an electronic case report form in REDCap by the study clinician and laboratory test result reports will similarly be captured by laboratory personnel.

All reports form part of source documentation and will be filed in participant folders.

Outcome classification conducted by the clinical committee will be done using standard outcome classification forms, which will be captured into an electronic case report form in the database.

7.2 DATA MANAGEMENT

Information captured into electronic case report forms, is uploaded in real time to a secure, password protected database, hosted by Stellenbosch University. The database will be managed by the database manager of the study team, who will oversee regular data checks for missing data and data validation.

7.3 DATA STORAGE

Informed consent documents and source documentation, including clinical result reports, will be stored in the regulatory file and participant files in access controlled, locked cabinets at the study site. Records will be kept for a minimum of 15 years, in compliance with local and international policies.

A daily automated back-up of the database onto an off-site back-up server will done. In addition, a 2 weekly manual back-up of the data onto an external hard drive will be done by the database managers.

8. ASSESSMENT OF SAFETY

An adverse event(AE) is any untoward medical or psychological occurrence in a human research participant, including any abnormal laboratory finding, symptom or disease, and which does not necessarily have a causal relationship with the research or any risk associated with the research. It also includes any event that can affect research participants or data integrity negatively, or that has the potential to impact negatively on members of the research team, or on the project as a whole, and that is deemed significant by the investigator.

A serious adverse event (SAE) is an adverse event that, in the view of either the investigator or sponsor, is life-threatening or results in death, hospitalisation, persistent or significant disability, a birth defect or requires intensive intervention to prevent permanent impairment or any of the previously mentioned outcomes.

AEs/SAEs can be considered related or unrelated to study procedures. As this is not an interventional study, we do not expect clinical AEs or SAEs to be related to any study procedures. All SAEs will be reported in a standardized way.

Additional reporting of adverse events to the EDCTP will be done according to their reporting requirements. All SAEs will be reported for the whole study period and even after the study has been completed, if the study team becomes aware of SAEs potentially related to study procedures. The principal investigator

should be notified of the SAE immediately. SAEs should be captured on a SAE form, which will be filed in

the study regulatory file. Additionally, SAEs will be reported to the Stellenbosch University Human Research Ethics Committee within 7 calendar days.

